Five phases of the development of acute GvHD have been described ([Socié 2019](#)). The first phase, priming of the immune response, is initiated by the underlying disease and the conditioning regimen used to prepare for transplantation. Damage to host tissues results in the secretion of pro-inflammatory cytokines that can increase the expression of adhesion molecules, co-stimulatory molecules, major histocompatibility complex (MHC) antigens and chemokines - all of which activate host antigen presenting cells (APCs). The second phase, T-cell activation and co-stimulation occur when donor T cells proliferate and differentiate in response to host APCs. The incidence of acute GvHD is directly related to the degree of mismatch in human leukocyte antigen (HLA) determinants such as MHC class II and I and minor histocompatibility antigens (MiHA). Additional donor/host differences, such as polymorphisms in proteins connected with innate immunity (NOD2), in the Toll-like receptor family, and in cytokine genes, are also believed to contribute to acute GvHD risk. The third and fourth phases of acute GvHD include alloreactive T-cell expansion and differentiation followed by the migration of activated T-cells to GvHD target tissues such as the gut, liver, skin, and lung and the recruitment of other effector leukocytes. In the last phase of acute GvHD development, effector T-cells initiate the destruction of target tissues via exposure to the cell surface and the release of soluble immune effectors. The resultant tissue damage leads to an increase in inflammatory signals and propagation of the cytokine storm.

Classic acute GvHD generally develops within the first 100 days after myeloablative HSCT and typically affects the skin, gastrointestinal (GI) tract, and liver. In the setting of prophylaxis with immunosuppressants, Grade II-IV acute GvHD occurs in 25-60% of matched related transplant recipients and in 45-70% of matched unrelated recipients ([Ho 2001](#)). Although less common with myeloablative transplants, late onset acute GvHD may occur after 100 days post HSCT. The incidence of acute GvHD increases with increasing HLA mismatch between donor and recipient, unrelated donor transplant, female donor to male recipient and use of a total body irradiation (TBI) containing preparatory regimen. The development of Grade III/IV acute GvHD is

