## 7 SUBJECT POPULATION

### 7.1 Inclusion Criteria

All subjects (including CIBMTR control group, except where noted) must meet the following criteria:

1. Ages  $> 18$  and  $\leq 65$  years of age
2. Has a hematologic malignancy as defined below and is considered a candidate for allo HSCT:
  - a. Acute myelogenous leukemia (AML) in first or subsequent morphologic complete remission
  - b. T or B cell acute lymphoblastic leukemia (ALL) in first or subsequent complete morphologic remission
  - c. Myelodysplastic syndrome (MDS), chronic myelomonocytic leukemia (CMML), myeloproliferative disorder (MPD) including myeloid metaplasia and myelofibrosis and are currently with  $< 10\%$  blasts in bone marrow
  - d. CML subjects who have received prior treatment including at least one tyrosine kinase inhibitor and are currently in chronic phase or with a complete hematologic remission but with evidence of cytogenetic or molecular relapse
3. Must have adequate organ function as defined below (RGI-2001 treatment group only):
  - a. Cardiac function: Left ventricular ejection fraction at rest  $\geq 45\%$
  - b. Liver function: total bilirubin  $< 1.5$  x upper limit of normal (ULN); alanine aminotransferase (ALT) and aspartate aminotransferase (AST)  $< 2.5$  x the ULN. Patients who have been diagnosed with Gilbert's Disease or malignant involvement are allowed to exceed the defined bilirubin value of  $1.5$  x the ULN
  - c. Serum creatinine  $< 2$  mg/dL or estimated creatinine clearance  $> 50$  mL/min calculated using the Cockcroft-Gault equation
  - d. Pulmonary: DLCO (corrected for hemoglobin) and/or FEV1  $\geq 50\%$
4. Considered suitable candidate for a myeloablative allogeneic or unrelated donor transplant based on institutional criteria
5. Subject must be receiving first allogeneic transplant from a single donor. Prior autologous transplant is acceptable
6. Transplant Donor:
  - a. Matched related donor (8/8): Molecular identity at HLA-A, -B, -C and -DRB1 by high-resolution typing
  - b. Unrelated donor ( $\geq 7/8$  allelic match): high resolution molecular typing at the following loci is required HLA -A, -B, -C and -DRB1
  - c. Meets institutional criteria for bone marrow or PBSC donation (see [Section 7.4](#))

7. Source of the Allograft:
  - a. Unmodified bone marrow or mobilized peripheral blood stem cell (PBSC) transplant, using granulocyte colony stimulating factor (G-CSF) as the mobilizing agent. Cord blood is not allowed

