### **7.3 Eligibility for the Control Arm**

Subjects in the control arm will be identified from subjects reported to the CIBMTR from U.S. centers and which agree to participate in this study. Control subjects must satisfy the inclusion and exclusion criteria of this study according to [Section 7](#).

Data for all eligible subjects in centers agreeing to participate in the study will be used to constitute the control database for this study.

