### **11.2 Enrollment Procedure for the Transplant Subjects in the Control Arm via the CIBMTR**

Data reported on pre-transplant Transplant Essential Data (TED) forms to the CIBMTR by participating centers will be monitored to screen subjects who fulfill the eligibility criteria ([Section 7](#)). Control subjects who fulfill eligibility criteria and who have a signed ICF to allow their data to be used for research will be assigned to the CIBMTR comprehensive data reporting track (CRF-track) and centers will be notified. Forms due requirements for the case report form (CRF) track will be implemented.

It is anticipated that a minimum of 250 transplant subjects will be enrolled to ensure sufficient subjects are comparable to the RGI-2001 treatment population.

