### 12.3.1 Analysis of Efficacy Data

The primary endpoint grades II-IV acute GvHD by Day 100 according to the MAGIC criteria will be compared between the study group and CIBMTR controls using logistic regression. The factors that will be considered for adjustment in this model include subject age, gender, donor age, type of donor (MRD, 8/8 URD 7/8 URD), source of allograft, diagnosis (AML, ALL, MDS, MPD including CMML), preparative regimen, GvHD prophylaxis regimen.

Secondary endpoints that will be modeled as binary outcomes will similarly be compared using logistic regression. Secondary endpoints that will be modeled as time-to-event outcomes will be compared using Cox regression.

Potential interactions of RGI-2001 and various factors will be examined by including appropriate factors into regression models.

Given that this is not a randomized study and that the intention is only to assess outcomes for a potential signal, no adjustments will be made for multiple comparisons. As such, a Type II error (or a false negative) is prioritized over a Type I error (or a false positive).

Binary exploratory outcomes will be summarized with proportions, continuous outcomes with means and medians, and time-to-event outcomes with Kaplan-Meier estimates or cumulative incidence estimates for endpoints with competing risks.

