6.4 Graft Source and Donor Characteristics

A table will be provided to summarize: donor/recipient sex matching, graft source, donor relationship to the subject, and donor/recipient CMV serostatus. A by-subject listing will also be provided.

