8.0 EVALUATION OF EFFICACY PARAMETERS

All efficacy analyses will be performed on the Safety Analysis Population. As noted above, outcomes will ultimately be compared to data obtained from the CIBMTR and details of this comparison are contained in a separate SAP that is specific to this goal. Methods for estimation of efficacy parameters are provided below without mention of the methods that will be used for comparing efficacy parameters to the CIBMTR data.

Binary outcomes will be summarized with proportions, continuous outcomes with means and medians, and time-to-event outcomes with Kaplan-Meier estimates or cumulative incidence estimates for endpoints with competing risks.

Definitions of occurrence and timing of outcomes are described below.

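### The adjustment factors named for the non-randomised acute GvHD comparison omit donor-recipient sex match, a risk factor the protocol itself names (low severity, almost free to correct)

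*Protocol*

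**What the plan says.** The study is open label and not randomised. About 50 treated subjects are compared with at least 250 CIBMTR controls from participating centres, transplanted in the same time window (Protocol 6.3, 6.6).

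For the primary endpoint, Protocol 12.3.1 and the synopsis specify logistic regression: "The factors that will be considered for adjustment in this model include subject age, gender, donor age, type of donor". Donor type separates matched related donors from unrelated donors at the 8/8 and 7/8 match levels. The list goes on to source of allograft, diagnosis, preparative regimen and GvHD prophylaxis regimen. Gender stands between subject age and donor age, so it reads as the recipient's.

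Protocol 4.1.1 says acute GvHD incidence rises with HLA mismatch, unrelated donor, "female donor to male recipient and use of a total body irradiation (TBI) containing preparatory regimen".

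SAP 6.4 already plans to describe the variable for treated subjects: "A table will be provided to summarize: donor/recipient sex matching, graft source". SAP 8.0 leaves the comparison with the registry elsewhere: "details of this comparison are contained in a separate SAP that is specific to this goal". That second SAP is not among the documents available here.

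**The concern.** Without randomisation, covariate adjustment is a main safeguard for the primary comparison. The protocol identifies four determinants of the outcome and provides terms for three. Recipient gender cannot stand in for the fourth, because the risk lies in the combination of donor and recipient: a male recipient may have a donor of either sex. If the realised proportion of female-to-male pairs differs between the groups, the named model attributes part of that difference to RGI-2001. Naming the term in advance also avoids having to choose it after open-label outcomes are known.

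**Working it through.** **Text check.** Each risk factor in Protocol 4.1.1 against the list in 12.3.1:

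| Risk factor named | Term in the list |
|---|---|
| HLA mismatch | donor type (8/8 vs 7/8) |
| Unrelated donor | donor type (MRD vs URD) |
| TBI-containing regimen | preparative regimen |
| Female donor to male recipient | none |

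**Figure in the plan.** None to reproduce: the power table is redacted. What follows is an illustration.

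**Inputs from the documents.** 50 treated and 250 controls (6.6); one-sided .10 (synopsis); acute GvHD 25-60% with matched related and 45-70% with matched unrelated donors (4.1.1).

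**Assumed inputs.** Sex-match odds ratio (OR) 1.3, 1.5 or 2.0; female-to-male pairs 20% on average, so a 10-point gap is 15% vs 25%; 55% male recipients in both groups; 45% acute GvHD among controls; no drug effect.

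**Bias at a 10-point gap, more such pairs in controls.** Let p0 be the risk without the pairing and p1 = OR x p0 / (1 - p0 + OR x p0) the risk with it. Solve .75 p0 + .25 p1 = .45.

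- OR 2.0: p0 = .4071 and p1 = .5787. The treated rate is .85 x .4071 + .15 x .5787 = .4328. The crude treatment OR is (.4328/.5672) / (.45/.55) = .933.
- A logistic fit to the expected cell counts gives:

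| Sex-match OR | Risk difference (points) | Gender-adjusted OR | Same gap reversed | With sex match added |
|---|---|---|---|---|
| 1.3 | 0.65 | .974 | 1.027 | 1.000 |
| 1.5 | 1.01 | .960 | 1.042 | 1.000 |
| 2.0 | 1.72 | .932 | 1.072 | 1.000 |

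At control rates of 25%, 45% and 70% the risk difference stays between 0.5 and 1.7 points.

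**Against the noise.** SE of the log OR is about sqrt[1/(50 x .2475) + 1/(250 x .2475)] = .311, where .2475 = .45 x .55. The bias is |ln .974| = .026 to |ln .932| = .070. Divided by .311, that is .08 to .23 SE.

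**What recipient gender absorbs.** With an equal male share, nothing: at OR 2.0 the crude and gender-adjusted ORs are .933 and .932. If males are 50% of treated and 60% of control subjects, with the same 10-point gap, gender adjustment moves .933 to .959.

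**How often chance alone gives such a gap.** SD of the gap = sqrt[.2 x .8 x (1/50 + 1/250)] = .062. In simulation, a gap of 10 points or more in either direction occurs in about 11% of trials, and 20 points or more in about 0.1%.

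**Error rate.** 20,000 simulated trials per setting, chance imbalance only, one-sided .10 (Monte Carlo SE .002). Without the term the error is .102 (OR 1.5) and .096 (OR 2.0); with it, .103 and .096. In runs with a realised gap of 8-12 points favouring RGI-2001 (Monte Carlo SE about .008), it is .113 and .133 without the term, against .094 and .099 with it. With the gap the other way it is .075 and .054, against .099 and .083.

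**The case against.** The strongest reply is that the list is not the final model. It is worded as factors to be considered, and the comparison SAP may already contain sex match. Both points stand. A reader might infer that the comparison will ignore sex match; the documents show only that the protocol does not name it.

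A second reply is that little follows from the omission. No mechanism for systematic imbalance is apparent: donor sex is not an eligibility criterion, and controls share centres and time window. A reader might infer a bias in favour of RGI-2001 or an inflated false-positive rate. Neither is supported. The direction is unknown, and under chance imbalance the error stays near .10. The conditional error rates apply only if a gap of that size occurs. The trial seeks a signal at one-sided .10, against which 0.1 to 0.2 SE is small.

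A third reply is that the illustration is favourable to the point. The OR, prevalence and male share are assumed. With equal male shares gender can absorb nothing, and the exact return to 1.000 follows because sex match is the only omitted cause in the model. This also stands, and is why the range starts at OR 1.3 and the unequal-male-share case is shown.

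A reader might also make more of control eligibility. Several summary statements (for example Protocol 6.3 and 12) say controls meet all eligibility requirements, while inclusion 3 reads "Must have adequate organ function as defined below (RGI-2001 treatment group only". It is tempting to infer that controls are less fit and that survival outcomes favour RGI-2001. The documents do not carry that. Section 7.1 opens with "All subjects (including CIBMTR control group, except where noted) must meet the following criteria", and 7.3 says "Control subjects must satisfy the inclusion and exclusion criteria of this study according to" Section 7, so Section 7 governs. Controls must still be suitable for myeloablative transplant and have KPS of at least 60, and planned reduced-intensity conditioning is excluded for all. The documents do not mention registry organ-function data. What remains is a separate editorial reconciliation. It gives no ground for an organ-function sensitivity analysis, and adding KPS as a covariate would be a preference.

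**Conclusion.** The omission is real and can be checked within the protocol: of the risk factors it names for its primary endpoint, female-to-male pairing alone has no adjustment term. Its expected effect is modest. A realised 10-point gap would leave a spurious treatment OR of about .97 to .93, or 1.03 to 1.07, conditional on the assumed sex-match OR of 1.3 to 2.0, 20% prevalence, 45% acute GvHD rate and equal male share. Recipient gender removes part of this if the male share also differs. The gain from the extra term is a less biased estimate in the trial as it turns out; there is no inflated error rate to repair. This is a low-severity, nearly free improvement, and it falls away if the comparison SAP already includes the term.

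**What to change.** Add donor-recipient sex match (female-to-male versus other) to the adjustment factors, alongside gender, in Protocol 12.3.1, the synopsis and the CIBMTR-comparison SAP, unless that SAP already has it.

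First confirm that donor sex is recorded for controls. This is plausible but not stated: donor age is already on the list, so donor-level data are needed anyway, and Protocol 11.2 says eligible consenting controls "will be assigned to the CIBMTR comprehensive data reporting track (CRF-track").

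The cost is one model term. The SE of the treatment log OR rises by 0.6-1.1% on average under chance imbalance and by 0.6-1.5% at a 10-point gap. Simulated power at a treatment OR of 0.5 is .798-.799 without the term and .799-.803 with it. Those runs contain treatment, gender and sex match only, so they indicate the cost and do not reproduce the plan's power.

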## 12.4 Suspension Rules Based on Safety (RRT, Graft Failure, and NRM)

Careful monitoring of safety will take place beyond the Safety Run-in Phase, with safety encompassing the outcomes grade 4-5 regimen-rated toxicity (RRT), graft failure, and NRM. The study will be suspended pending SRC review if there is sufficient evidence to suggest that the true failure rate for any of these outcomes is excessive. A true graft failure (as defined in [Section 9.4.1](#)) rate of 5% or higher is considered excessive ([Olsson et al](#)), a true Day-100 NRM rate of 10 or higher is considered excessive ([Styczyński et al](#)), and a true Day 30 grade 4-5 RRT rate of 50% or higher is considered excessive (defined as any non-hematologic toxicity that occurs as a result of the transplant process including the preparatory regimen or RGI-2001 infusions). This rate is extrapolated from published results of D30 NRM ([Styczyński et al](#)) and increased further to encompass grade 4 events in the allogeneic myeloablative setting based on site experience. Sufficient evidence will be taken to be a lower limit to the one-sided 80% confidence interval associated with an estimated failure rate that exceeds the appropriate level listed above. [Table 3](#) below shows observed outcomes that would trigger suspension, and [Table 4](#) below summarizes the operating characteristics of the listed suspension rule separately for each safety endpoint (e.g., separately for Day 30 grade 4-5 RRT, graft failure, Day-100 NRM).

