**Figure 2 DLT Schema**

## 6.2 Expansion Phase

Once a dose/schedule is determined by the SRC to have an acceptable safety/PK profile, enrollment will continue in the Phase 2 Expansion Phase and be extended to all sites.

Accrual is targeted at 50 subjects who receive the dose deemed as acceptable from the Safety Run-in Phase (44 in the Expansion Phase, 6 from the Safety Run-in Phase at the dose used in expansion). All subjects in the Expansion Phase who receive at least one dose will be considered in all efficacy and safety analyses.

Subjects will receive open-label RGI-2001 at a dose of 100µg/kg (unless an alternative dose and/or schedule is chosen by SRC), via 30-minute intravenous (IV) infusion on a weekly basis for 6 doses (or an alternative dose/schedule as determined in the run-in phase) in addition to a SOC GvHD prophylactic regimen. The first dose will be administered on Day 0 at approximately 30 minutes and no later than 1 hour after HSCT infusion. Subsequent doses will be administered weekly, on Days 7, 14, 21, 28 and 35.

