## 8.6 Administration and Dosing Regimen

All subjects will receive 6 weekly doses of RGI-2001 100 µg/kg via IV administration over 30 minutes. Weight should be taken within one day of dosing and the dosage of RGI-2001 should be verified to be the same as the planned dose. The dosage of RGI-2001 will be diluted in 50 ml 0.9% normal saline and the first dose will administered intravenously at approximately 30 minutes and no later than 1 hour after completion of the allogeneic HSCT on Day 0 (study Day 1 if transplant occurs over 2 days). If cytokine release/infusion reaction is observed during or after HSCT, then RGI-2001 should be postponed until at least 30 minutes after the reaction has resolved. Subsequent RGI-2001 administrations should be administered on Days 7, 14, 21, 28, and 35 +/- 1 day. Pre-medications should not be administered prophylactically. However, if a grade 2 cytokine release is observed, pre-medication with an antihistamine (e.g., diphenhydramine), an anti-pyretic (e.g. acetaminophen) and corticosteroids (e.g., 4 mg dexamethasone or equivalent) should be administered. Consideration may be made to administer premedication for Grade 1 cytokine release, depending on the constellation of symptoms. In addition, the SRC may recommend pre-medications in all current and future subjects depending on safety reviews.

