### ***8.10.1 Safety Run-in Phase***

RGI-2001 will be administered at a dose of 100 µg/kg IV weekly for 6 doses. There are no dose reductions or escalations in this portion of the study except as recommended by the SRC at the end of the run-in period. Each individual infusion is allowed to be delayed up to 2 weeks for ongoing grade 3+ AEs, regardless of causality. However, if a subject enrolled in the run-in period is not able to receive at least 50% of RGI-2001 doses during the DLT window for reasons other than toxicity, then that subject will be replaced. Subjects requiring delay of an infusion of > 2 weeks should be discontinued from treatment.

Subjects enrolled in the Run-in Phase beyond the DLT window who meet DLT criteria should be discontinued from study treatment. Supportive care should be administered as appropriate.

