## 10.2 Adverse Event Reporting

The reporting period for non-serious adverse events starts at the commencement of the infusion of RGI-2001 on Day 0 and continues for at least 30 days following the last dose of study drug. Medical conditions that start after the ICF is signed, but before the first dose of study drug should be recorded on the medical history eCRF.

If an AE remains unresolved 30 days following the last dose of study drug, the subject will be followed, at the investigator’s discretion, until resolution of the event. Resolution is defined as return to baseline status or stabilization of the condition with the expectation that it will remain chronic.

Adverse events (including laboratory abnormalities that constitute AEs) should be described using a diagnosis whenever possible, rather than individual underlying signs and symptoms. When a clear diagnosis cannot be identified, each sign or symptom should be recorded as a separate AE.

The Investigator should ask the subject non-leading questions to determine if any AEs have occurred during the study, since the last study visit. Adverse events may also be recorded when they are volunteered by the subject, or through physical examination, laboratory tests, or other clinical assessments.

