**Table 3 Suspension Rules for Grade 4-5 RRT, Graft Failure, and Day-100 NRM**

Safety outcome	Occurrences that would trigger suspension rule and SRC review
Day 30 grade 4-5 RRT	3 RRT of first 3 pts, 4 RRT of first 5 or fewer pts, 5/6, 6/7-8, 7/9-10, 8/11-12, 9/13, 10/14-15, 11/16-17, 12/18-19, 13/20-21, 14/22, 15/23-24, 16/25-26, 17/27-28, 18/29-30, 19/31-32, 20/33-34, 21/35, 22/36-37, 23/38-39, 24/40-41, 25/42-43, 26/44-45, 27/46-47, 28/48-49, 29/50
Graft Failure	2 failures of first 16 pts or fewer, 3/17-30, 4/31-46, 5/47-50
Day-100 NRM	2 failures of first 8 pts or fewer, 3/9-15, 4/16-23, 5/24-31, 6/32-39, 7/40-47, 8/48-50

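### The numerical Grade 4-5 RRT suspension rule closes at Day 30, before the sixth infusion on Day 35, so a non-fatal Grade 4 non-hematologic event after the last dose enters no pre-specified suspension count.

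*Protocol*

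**What the plan says.** Protocol Section 12.4 sets three numerical suspension rules for monitoring beyond the Safety Run-in Phase: RRT, graft failure and NRM. For RRT, "a true Day 30 grade 4-5 RRT rate of 50% or higher is considered excessive". RRT is defined as "any non-hematologic toxicity that occurs as a result of the transplant process including the preparatory regimen or RGI-2001 infusions", with no infusion excepted. The Table 3 row is labelled "Day 30 grade 4-5 RRT". Section 12.4 says that the 50% rate was extrapolated from published Day 30 NRM and raised to take in Grade 4 events.

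On dosing, Section 6.2 says "Subsequent doses will be administered weekly, on Days 7, 14, 21, 28 and 35", after a first dose on Day 0. Section 8.6 adds the visit window: "Subsequent RGI-2001 administrations should be administered on Days 7, 14, 21, 28, and 35 +/- 1 day". In the run-in, Section 8.10.1 allows postponement: "Each individual infusion is allowed to be delayed up to 2 weeks for ongoing grade 3+ AEs, regardless of causality". In the expansion, Section 8.10.2 provides for doses to be held after certain Grade 3 events.

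Adverse event collection runs longer than the RRT count. Under Section 10.2 it "continues for at least 30 days following the last dose of study drug".

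**The concern.** The definition and the counting window do not cover the same exposure. RRT takes in toxicity from all six infusions, but the window shuts before the sixth is given. Human experience summarised in Protocol Section 4.5 is single-dose, and repeat dosing is what this study adds. Section 12.4 holds the only numerical rule for severe, non-fatal, non-hematologic toxicity in the 44 planned expansion subjects. Followed exactly, it leaves out the last dose. Grade 4 events after that dose would be recorded but could not trigger the pause that the section is meant to provide.

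**Working it through.** **1. Timing.** Day 0 is the day of transplant and first dose. Section 12.4 does not state what Day 30 is counted from. I take it as 30 days after transplant, which fits the study's day numbering and the Day 30 NRM source of the 50% rate.

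Days inside the window = 30 − infusion day, with a minimum of 0.

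| Infusion | Day | Days inside window |
|---|---|---|
| 1 | 0 | 30 |
| 2 | 7 | 23 |
| 3 | 14 | 16 |
| 4 | 21 | 9 |
| 5 | 28 | 2 |
| 6 | 35 | 0 |

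With the ± 1 day window, the fifth infusion has 1 to 3 days inside. The earliest sixth infusion is 35 − 1 = Day 34, which is 4 days after the window closes. Delays can only move doses later, so no permitted schedule brings the sixth infusion into the count.

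**2. Do the other rules fill the gap?**
- Graft failure (Protocol 9.4.1) is lack of myeloid engraftment, not a count of Grade 4 toxicity.
- NRM (SAP 8.5) is death without prior relapse. A non-relapse death after dose 6 and by Day 100 counts; a non-fatal Grade 4 event does not.
- The dose-limiting toxicity window (Protocol 6.1.1) is also 30 days from the first dose and applies to the run-in only.
- The review of safety after all six doses (Protocol 6.1) covers the six run-in subjects.

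**3. Reproducing the plan's figures.** Section 12.4 requires the lower limit of a one-sided 80% confidence interval to exceed 50%. With an exact limit, the boundary at n patients is the smallest r with P(X ≥ r | n, 0.50) < 0.20. For example, at n = 45, P(X ≥ 26) = .186 and P(X ≥ 25) = .276, so r = 26, as Table 3 prints. The whole RRT row matches from n = 3 to n = 50.

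Applying that boundary after every patient by exact recursion gives:

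| True RRT rate | n | Table 4 | Recomputed |
|---|---|---|---|
| .30 | 10 / 25 / 45 | .05 / .05 / .10 | .050 / .054 / .054 |
| .70 | 10 / 25 / 45 | .72 / .94 / .99 | .737 / .927 / .989 |

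The .30, n = 45 cell does not reproduce: .10 is printed and .054 is obtained. This is separate from the timing point.

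**4. What the gap could hide (assumed rates).** Let 30% have RRT by Day 30 and a fraction q of the remainder have a first Grade 4 RRT later. Total rate = .30 + .70q. The written rule sees only the 30%.

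| q | Total rate | Written rule, by 45 patients | Same boundary, later events counted |
|---|---|---|---|
| 0 | .30 | .054 | .054 |
| .10 | .37 | .054 | .126 |
| .20 | .44 | .054 | .271 |
| .30 | .51 | .054 | .512 |

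**5. Price of a longer window with the boundary unchanged.** If background events alone raise the true rate, the trigger probability by 45 patients is .054 at 30%, .10 at 35%, .18 at 40% and .30 at 45% (assumed rates, all below the 50% called excessive).

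**The case against.** The strongest reply is that the window is deliberate. Day 30 appears in both the text and Table 3, the 50% rate comes from a Day 30 source, and RRT also covers the preparative regimen and the transplant. Window and benchmark therefore match. That stands as a reason not to lengthen the window while keeping 50% by default. It does not explain why the definition includes every infusion while the count excludes the last.

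Three stronger readings are tempting, and the documents do not support them.
- **That late toxicity can never suspend the study.** The SRC monitors safety throughout and may make recommendations on continuation (Protocol 6.4), and the sponsor may terminate on the incidence or severity of adverse events (7.5.1). A related Grade 4 event also ends that subject's treatment (8.10.2). These routes are real, but none has a numerical study-level threshold.
- **That the rule is blind to repeat-dose toxicity.** Infusions 2 to 4 have 23, 16 and 9 days inside the window. The gap is dose 6 and nearly all follow-up of dose 5.
- **That Table 4 is wrong because of the window.** Its RRT rows give the trigger probability for a stated rate and carry no day label, so they hold for whatever window defines that rate.

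The size also depends on how much toxicity comes late, which the documents do not say. Going from 30% at Day 30 to 50% overall needs .20/.70 = 29% of event-free patients to have a later event; reaching 70% needs .40/.70 = 57%. Those are extreme cases. With q of 10% or 20%, counting late events raises the trigger probability only to .126 or .271, largely because the threshold is as high as 50%.

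**Conclusion.** The point holds for the pre-specified numerical rules. On the protocol's own dates, a non-fatal Grade 4 non-hematologic event after dose 6 cannot trigger any of them. Non-relapse deaths still count under Day-100 NRM, and discretionary SRC or sponsor action remains. The timing result needs only Day 30 to be measured from transplant. The probabilities rest on assumed rates and show direction and scale; they do not predict what the trial will see. This is more than a missing detail, because the rule as written omits the final dose of the schedule under test. It should be corrected.

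**What to change.** Reconcile the RRT definition and counting window in Section 12.4 and Table 3 with dosing through Day 35, and state what Day 30 is measured from. Two routes are open:

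1. Count Grade 4-5 RRT through the existing adverse event reporting period, at least 30 days after the last dose (about 35 + 30 = Day 65 if on time). The present boundary should not be carried over by default: justify a reference rate for the longer window and recompute Tables 3 and 4.
2. Keep the Day 30 rule and add a separate count, with its own justified rate, for the later period.

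Either way, correct or explain the Table 4 entry of .10 at a true rate of .30 and n = 45.

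The cost is wording and two tables; the data are already collected. The downsides are more false suspensions from background late events (the .054 to .30 range above if the boundary is left alone) and, under route 1, a window that closes about five weeks later for each patient (65 − 30 = 35 days). A false trigger means a pause pending SRC review. The change concerns study-level monitoring only and leaves dose, schedule and individual treatment rules untouched.
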